3.7 Study Outcomes

Primary Endpoint: The primary outcome will be the proportion of patients for which Oncotype DX ® is ordered, defined as the number of patients with Oncotype DX ® orders divided by the number of patients eligible for Oncotype DX ® testing.

Secondary Endpoints:

Frequency and type of chemotherapy used will be collected from the patient's electronic medical record as will timing to start chemotherapy, radiation therapy and endocrine therapy. Prognostic risk scores, including Magee formulae, Gage and Tennessee equations will be calculated using patient and tumour characteristics. These scores will also be compared with Oncotype DX ® results when performed. Physician questionnaire results will be used to assess physician comfort when making systemic therapy decisions.

Economic analysis:

We will conduct a cost analysis and compare total health system costs before and after the model implementation from the Ontario government's perspective.

The cost components will include Oncotype DX cost (C\$4380), adjuvant chemotherapy cost and other health services costs. We assume that the PREDICT 2.1 tool is readily available at no cost. The cost associated with other health services among patients who receive and those who do not receive adjuvant chemotherapy (including cost of cancer clinic, in-patient services, physician billing, chemotherapy, endocrine therapy, supportive drug, home care, in-patient and emergency department costs) [26] will be obtained from a concurrent cohort study and Canadian sources. Based on this analysis, we will then extrapolate the cost findings to the entire population of Ontario to report the financial implications of our intervention to Cancer Care Ontario.

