1.0 SUMMARY

A broad range of prognostic and predictive tools are available for patients with newly diagnosed early stage hormone receptor positive, Her2 negative breast cancer. These range from free and publicly available mathematical algorithms (e.g. NHS Predict, Magee formulae, Gage and Tennessee equations) that incorporate standard pathology results, through to expensive genomic tests (e.g. Oncotype DX ® and Endopredict ®). It is not known how the use of these different scores affects physician decision making with respect to ordering genomic tests, nor how well these algorithms predict for the results of Oncotype DX ® in the real-world setting. This pragmatic study will help to answer these questions.

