2.0 INTRODUCTION

A broad range of prognostic and predictive tools have been developed for patients with newly diagnosed early stage breast cancer [1-4]. These include free and publicly available algorithms (e.g. NHS Predict 2.1 [5], Adjuvant online! [6-8], the Magee equations (1,2,3) [9, 10], Gage [11] and University of Tennessee probability models [12]), IHC4 [13] that incorporate standard readily available pathology results to genomic tests such as Oncotype DX ®, MammaPrint ®, EndoPredict ®, Breast Cancer Index ®.

Oncotype DX ®

In recent years there has been widespread introduction of multigene genomic assays and immunohistochemistry (IHC)-based scores to improve clinical decision making for patients with early stage hormone receptor positive, Her2 negative breast cancer [14-18]. The Oncotype DX ® Recurrence Score (ODX; Genomic Health, Redwood City, CA) is a widely used prognostic and predictive tool to guide treatment in patients with node-negative, estrogen receptor (ER) positive and/or progesterone receptor (PR) positive disease. Among genomic tests, Oncotype DX ® and MammaPrint ® are prospectively validated at present time [19, 20]. While Oncotype DX ® use has been shown to reduce the overall use of adjuvant chemotherapy, its use presents challenges which include: its expense (C\$4380) restricting its use to resource rich countries significantly affects its potential for use in developing countries, in addition, as the test requires a tissue specimen to be sent to a central laboratory thereby increasing

local pathology service demands, it leads to a delay in making treatment decisions. Oncotype Dx use also results in higher odds of chemotherapy use in patients with small node-negative cancers, lower odds of use of chemotherapy in node-positive or large node-negative disease, and an increase in the proportion of test requests in the traditional intermediate risk group (i.e. Oncotype DX ® Recurrence Score (RS) of 18-30) the group for which until recently there were no definitive answers with respect to the benefits of chemotherapy [16, 20].

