While the results of the TAILORx trial showed that overall patients in the intermediate risk group derived no additional benefit from chemotherapy, the subsequent subgroup analyses have added further confusion for patients and health care providers [20]. In this trial, patients in the intermediate risk group (adjusted to 11-25 for the trial design) were randomised to endocrine therapy with or without chemotherapy. This trial included 9719 patients aged 18-75 with 1.1-5 cm primary tumours, or 0.4-1.00 cm tumors with unfavourable features. Of the randomised patients 62% had 1.1-2 cm cancers, 80% had low-intermediate grade tumours and 68% were considered to have clinically low risk disease [6-8]. The results showed that postmenopausal (defined as those >50 years of age) derived no benefit from adding adjuvant chemotherapy to endocrine therapy with Oncotype DX ® RS of 11-25. While in patients aged 50 and under there appeared to be some benefit for chemotherapy if they had “high”-intermediate Oncotype DX ® RS of 21-25. The final recommendations were that for patients older than 50 years with Oncotype DX ® RS of 0-25, there is no benefit of

adjuvant chemotherapy, while for those aged 50 years or younger Oncotype DX® RS of 21-25 there was a 6.3% benefit in invasive disease-free survival at 9 years from addition of adjuvant chemotherapy. Furthermore, Oncotype DX® does not routinely incorporate classic histo-pathological data and could predict the same benefit from chemotherapy for a patient with 0.6 cm and 5.0 cm breast cancer while the benefit of chemotherapy is substantially more for a patient 5.0 cm breast cancer. This is reflected in a recent analysis of the TAILORx data which incorporates clinical risk demonstrating that clinical risk is prognostic and patients with lower clinical risk had a lower magnitude of benefit from treatment [21].

While the TAILORx results have received significant media attention, we believe there are important unanswered questions and potential limitations concerning the widespread adoption of Oncotype DX®. Many of these were raised by the study discussant at the 2018 ASCO meeting [22]. These included:

1. The study failed to evaluate which patients do not need the Oncotype DX® test performed.
2. Decision points for patients with newly diagnosed breast cancer are performed at baseline (addressed by TAILORx) and the duration of endocrine therapy is not addressed [23].

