4.0 STATISTICAL ANALYSIS

The primary analysis will be based on a hierarchical logistic regression analysis, with time period (pre-intervention versus post-intervention) as the primary covariate of interest. For this model, patient characteristics are considered nested within treating physician, which is nested within treatment centre. Adjustments will be performed for baseline characteristics. From our survey, it was evident that there was significant variability between centres (and between physicians) for ordering Oncotype DX. Data from Ottawa shows that approximately 15% of approximately 600 patients treated by 8 physicians have this test performed. In contrast, Kingston (5 physicians) sees around 200 eligible patients a year and Oncotype DX is ordered for around 65% of these patients,

Thunder Bay (3 physicians) sees around 70 patients a year and also tests around 65% of eligible patients, and Newmarket (3 physicians) sees around 130 eligible patients a year and Oncotype DX is ordered for around 75% of these patients. Windsor (3 physicians) and Kitchener (4 physicians) both see around 150 patients per year and orders Oncotype DX testing on 90% of eligible patients. Given concerns that use of hierarchical clusters may not sufficiently account for the substantial variability between sites, analyses will also be conducted by site, grouped by baseline rate of testing (i.e. Kingston, Thunder Bay and Newmarket will be combined, as will Windsor and Kitchener; Ottawa will be a separate group on its own). A similar analysis will be performed using hierarchical logistic regression. In addition, key supportive analyses will also be performed using a two-sample chi-square test within each site separately, comparing the change in proportion of patients for which Oncotype DX is ordered for each physician (i.e. post-intervention proportion – pre-intervention proportion for physician A, B, C, ...).

Analyses of secondary endpoints will be performed globally across all sites combined, and for each site individually. The chi-square test or Wilcoxon rank sum test will be used as appropriate for categorical or continuous endpoints respectively. Results will be presented using tables and figures, and exact confidence intervals will be constructed for outcomes of interest. Bootstrapping may be used for estimation purposes if required. All tests will be two-sided and statistical significance will be defined at the $\alpha=0.05$ level.

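### The comparison of Magee, Gage and Tennessee results with Oncotype DX is left to chi-square or rank-sum tests, with no accuracy measure and no threshold, so as planned it does not estimate how well the algorithms predict the Recurrence Score

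*Combined protocol and SAP*

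**What the plan says.** Section 3.7 lists the comparison under Secondary Endpoints. Its full specification is one sentence: "These scores will also be compared with Oncotype DX ® results when performed".

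Section 4.0 states the method for secondary endpoints, globally and by site: "The chi-square test or Wilcoxon rank sum test will be used as appropriate for categorical or continuous endpoints respectively". It adds that "exact confidence intervals will be constructed for outcomes of interest" and that "Bootstrapping may be used for estimation purposes if required", without naming the quantities. Tests are two-sided at 0.05.

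The purpose is stated elsewhere. The summary says it is not known "nor how well these algorithms predict for the results of Oncotype DX ® in the real-world setting", and that the study will help to answer this. The end of the PREDICT 2.1 text in section 2.0 also promises further validation of the algorithms.

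RS bands appear only in the background in section 2.0: the "traditional intermediate risk group (i.e. Oncotype DX ® Recurrence Score (RS) of 18-30"; then, for TAILORx, "In this trial, patients in the intermediate risk group (adjusted to 11-25 for the trial design"; then 0-25 for patients over 50 and 21-25 for patients aged 50 or under. No analysis uses any of them. Table 1 gives input cut-points for the Gage algorithm (PR >1%, ER >20%), but nowhere does the plan say which algorithm result would count as a prediction of low or high RS.

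**The concern.** The algorithm result and the RS are two measurements on the same patient, and the question is how well one predicts the other. That calls for a paired agreement measure or an accuracy measure such as sensitivity or negative predictive value (NPV). A p-value for association, or for a difference in location, is neither. A weak algorithm can pass a chi-square test easily. A rank-sum test of score against RS can be non-significant for a useless score and significant for one that ranks patients very well.

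Two gaps add to this. With several RS bands in the background and none assigned, the threshold could be chosen after the data are seen, and section 4.0 makes no multiplicity adjustment. And RS is recorded only when a physician orders the test (section 3.8), so any accuracy figure describes a selected group, and selection differs sharply between sites. At stake is one of the two questions in the summary, though not the primary endpoint.

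**Working it through.** **1. Is there a figure to reproduce?** No. Section 5.0 covers only the pre/post comparison of ordering. Its figures reproduce (with continuity correction, 301, 150 and 185 per period are needed, against 300, 150 and 185 in the plan), but they do not bear on this endpoint.

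**2. How many patients would have an RS?** Section 5.0 volumes and testing rates, per six-month period before the intervention:

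| Group | Eligible | Tested |
|---|---|---|
| Ottawa | 300 | 300×0.15 = 45 |
| Newmarket, Kingston, Thunder Bay | 75+75+35 = 185 | 56.25+48.75+22.75 = 127.75 |
| Windsor, Grand River | 75+75 = 150 | 67.5+67.5 = 135 |
| All | 635 | 307.75 (48%) |

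Ottawa is 300/635 = 47% of eligible patients but 45/307.75 = 15% of those with an RS. With no change in ordering, two periods give 2×307.75 = 615.5 tested patients. If the odds of ordering halve at every site (post-intervention proportion = 0.5×odds/(1+0.5×odds)), the second period gives 245.0, for a total of 552.8. So about 553 to 616 of 1,270 patients would have an RS.

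**3. What do the two named tests show?** Simulation with 600 tested patients and 1,500 runs per row. Assumptions, none from the plan: bivariate normal algorithm score and RS on one scale with equal distributions; top 15% counted as high RS; lower half of the algorithm score labelled as not needing the test (skip). Rank sum compares the score with RS as two samples. Chi-square is applied to the 2×2 table of skip against high RS. NPV = 1 − (share of high RS labelled skip × 0.15)/0.50; at correlation 0.3 this is 1 − 0.315×0.15/0.50 = 0.906.

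| Correlation | Rank sum p<0.05 | Chi-square p<0.05 | High-RS patients labelled skip | NPV |
|---|---|---|---|---|
| 0 | 5.2% | 4.8% | 50% | 0.850 |
| 0.3 | 2.3% | 97.3% | 31.5% | 0.906 |
| 0.5 | 1.1% | 100% | 19.3% | 0.942 |
| 0.7 | 0.1% | 100% | 8.0% | 0.976 |
| 0.9 | 0.0% | 100% | 0.4% | 0.999 |

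Rank sum is non-significant for both the worthless and the excellent score. Its rejection rate falls below 5% as correlation rises because it treats paired values as independent. With correlation 0.9 and a shift of 0.3 SD it rejects in 100% of runs. Chi-square separates zero association from some, but not a score that mislabels 32% of high-RS patients from one that mislabels 0.4%.

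A second set-up, with 300 patients (about one period), 20% high on each measure and correlation 0.3, gives the same message: chi-square is significant in 72–79% of runs (depending on the continuity correction and the random seed), while mean kappa is 0.16 and only 33% of high-RS patients are flagged.

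**4. What would an accuracy measure give?** Exact 95% intervals for the fraction of algorithm-low patients whose RS is above the chosen threshold, on assumed counts:

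| Labelled low | 2% above threshold | 5% above threshold |
|---|---|---|
| 100 | 0.2–7.0% | 1.6–11.3% |
| 200 | 0.6–5.0% | 2.4–9.0% |
| 300 | 0.7–4.3% | 2.8–8.1% |

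If half of 553 to 616 tested patients were labelled low (276 to 308), the pooled interval would be close to the last row. Site groups would sit nearer the first row or wider.

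**The case against.** The strongest reply is that section 4.0 leaves room. It promises tables, exact intervals and, if needed, bootstrapping; a table of algorithm category by RS category with exact intervals would yield sensitivity and NPV. This stands against one tempting inference, that the study cannot show whether an algorithm identifies patients who do not need the test. RS is recorded and the scores are to be calculated, so the data can support it. But the phrase about appropriateness in section 4.0 only chooses between two tests by endpoint type, and the interval and bootstrap sentences name no quantity or threshold.

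Second, the rank-sum failure depends on testing score against RS as two samples, which the plan does not spell out. The test could instead compare algorithm scores between high-RS and low-RS patients, where its statistic is a rescaled AUC. With 300 patients, a gamma RS with mean 18 and a split at 25 (all assumed for illustration), that use rejects 4–5% of the time for an unrelated score and 100% for RS+4, with AUC 1.0. Both are right answers. This stands, but that use needs the missing RS threshold, and the plan does not say the AUC would be reported. Nor does the plan say that a non-significant result would be read as equivalence; it promises caution with secondary endpoints.

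Third, a reader might infer that one common RS threshold would count an RS of 21-25 in a younger patient as a correct low call. The documents do not support this. In both band systems cited (18-30 and 11-25) that range is intermediate, and no split at 25 is proposed.

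Finally, the comparison is missing from the objectives in section 3.6, and the remark about patients who do not need the test is a criticism of TAILORx. Both limit the weight of the point; the summary and introduction still state the question.

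**Conclusion.** The concern holds in this form: under the method stated for secondary endpoints, the comparison yields p-values for association or location shift and does not estimate predictive accuracy. No RS or algorithm threshold is attached to it, and the restriction to tested patients is not addressed. It is a defect of the stated method, not of the data, and it leaves the primary analysis untouched.

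That no measure or threshold is named rests on the text alone. The size rests on the simulation assumptions (normal scores, 15% high RS, half labelled skip, 600 patients). Other choices would move the percentages, but not the finding that a significant chi-square is compatible with very different error rates. The number with an RS rests on the section 5.0 volumes. Even with a proper accuracy measure, a result in tested patients would not by itself establish who among all eligible patients could go untested, least of all in Ottawa, where about 85% would have no RS.

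**What to change.** In section 4.0, exempt this endpoint from the chi-square/rank-sum rule and state:

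- For continuous surrogate scores (Magee): Bland-Altman bias and limits of agreement, with a concordance correlation.
- For categorical calls: kappa (weighted only with more than two ordered categories), sensitivity and NPV, with exact intervals for the proportions.
- Before analysis, the sponsor prespecifies and justifies the RS threshold or thresholds, says whether they differ by age given the age-dependent findings in its own background, and prespecifies the algorithm thresholds.
- Estimates apply to tested patients only and are shown by the three site groups already defined by baseline testing rate.

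The cost is some SAP wording and a small amount of code; age and RS are already collected. The downside is wide intervals in small subgroups, which should be reported as they are.

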overall survival benefit from different modalities of breast cancer treatment such as endocrine therapy and second/third generation adjuvant chemotherapy. It is the only breast cancer prognostic model currently available online and has been used over 1 million times. Although the recent version of the PREDICT model better predicts mortality for younger patients with breast cancer, it also has limitations. PREDICT was originally developed based on data from patients between 1999-2003 and since then multiple advances such as the use of trastuzumab and third generation adjuvant chemotherapy regimens which include taxane have improved outcomes. The model has since been updated to reflect these advances. In addition, PREDICT uses classic histo-pathological features to determine prognosis and data from meta-analysis to determine benefit based on population outcomes rather than genomic assays which assess individual genomic alterations in a patient's tumor. Furthermore, both these models do not incorporate patient's co-morbidities especially in an aging population with other chronic diseases.

In the current prospective trial, we will evaluate whether use of PREDICT 2.1 impacts physician decision making with respect to ordering Oncotype DX®, particularly in patients aged <50, and other important cancer care metrics including chemotherapy use, time to commencement of chemotherapy, and resource utilisation. This data will also be used to provide further validation of the algorithms in a real-world, multi-centre setting.

Alternative Trial Designs

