3.3 Study Procedures

Each site will have a different process for determining eligibility. Research staff at each site will be confirming Oncotype DX ® eligibility from pathology reports and will be working with New Patient booking staff (or similar) to get weekly/daily clinic lists of new patients whose tumors meet eligibly for Oncotype DX ® testing.

Patient tumours at each site will enter study screening when a complete pathology report is received. Once a patient tumour is deemed eligible, it is given a Study ID number. Pathology data is collected by study staff. At all points of the study, patients with eligible tumours will meet with their treating physician to discuss the individualised testing and treatment plan that is best for them.

Once the physician meets with the patient, we will also collect the chemotherapy treatment plan details.

After 3 months of activation, physicians will start completing a questionnaire for each new patient with an eligible tumour. Delaying the questionnaires for the first 3 months is to prevent bias.

After 6 months of activation, the physicians will receive a teaching session (Intervention) consisting of PowerPoint slides which will present an updated review on the benefits and limitations of Oncotype DX and PREDICT testing.

After this teaching session, study staff at each site will be using the pathology data to run the PREDICT tool for each patient and will provide the results to each physician prior to his/her meeting with each patient. Again after 3 months, we will re-introduce the physician questionnaire for the last 3 months of the study.

In summary:

Month 1 to 3: pathology and chemo data collected, NO physician questionnaire

Month 4 to 6: pathology and chemo data collected, PLUS physician questionnaire

Intervention teaching after 6 months of study activation

Month 7 to 9: pathology and chemo data collected, PREDICT 2.1 tool used, NO physician questionnaire

Month 10 to 12: pathology and chemo data collected, PREDICT 2.1 tool used, PLUS physician questionnaire

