3.8 Data Collection

Data collection begins when a pathology report is completed and deemed eligible for Oncotype testing under the Ontario criteria. The following information will be collected from the patient's electronic medical record:

- Eligibility for Oncotype DX ® (ODX) reimbursement by OHIP (histologically confirmed primary breast cancer, no prior chemotherapy, ER positive, PR positive or negative, HER2 negative, lymph node status negative or micro-invasive disease, tumour >1 cm in size (or if ≤1cm, must be grade 2/3 or have lymph node micrometastasis))

- Whether ODX was ordered and if so, the ODX recurrence score
- Data required for PREDICT 2.1 algorithm (age, menopause, ER/Her2/Ki67 status, tumor size, tumor grade, method of detection, number of positive lymph nodes)
- Which chemotherapy regimen was planned and what chemotherapy the patient received
- Time from medical oncologist visit to starting chemotherapy

Data collected will be de-identified (no patient identifiers) and will not be linked to the treating physician. Data will be entered by the CRA at each site into a secure study-specific database.

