5.0 SAMPLE SIZE

Sample size calculations for hierarchical regression models are difficult, as they require estimates of the number of clusters, the size of each cluster, the effect of intervention on each cluster separately and intra-cluster correlation. Without prior information, these estimates are unlikely to be accurate. Hence, statistical power and sample size calculations will be based on practical considerations.

It is hypothesized that if the use of PREDICT 2.1 decreases the odds of Oncotype DX ordering by approximately 50% or more, the usage of Predict 2.1 will be of clinical importance. It is known that approximately 300 patients are seen in a given six-month period in Ottawa, and approximately 15% of eligible patients undergo Oncotype DX testing. For the other centres, the values are 75 and 75% (Newmarket), 75 and 90% (Windsor), 75 and 65% (Kingston), 35 and 65% (Thunder Bay), and 75 and 90% (Grand River). Based on these estimates,

a simple, two-sided, $\alpha=0.05$, logistic regression model would have 80% power to detect an odds ratio of 0.46 (from 15% to 7.46%) in Ottawa, an odds ratio of 0.38 (from 90% to 77.4%) in Grand River/Windsor, and an odds ratio of 0.53 (from 70% to 55.4%) in Newmarket/Kingston/Thunder Bay. Overall, if one conservatively estimates at least 500 patients will be eligible pre-intervention and 500 patients will be eligible post-intervention, a simple logistic regression analysis would have over 80% power (2-sided, $\alpha=0.05$) to detect an odds ratio of 0.67, assuming that approximately 50% of patients undergo Oncotype DX testing in the pre-intervention period. Combined, these estimates give assurance that the sample size for this study is sufficient to capture clinically meaningful effects.

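### The algorithm scores are compared with Oncotype DX only in the roughly 48% of eligible patients who were tested, and nothing in the plan addresses the resulting risk of verification bias

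*Combined protocol and SAP*

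**What the plan says.** Section 3.7 lists, under secondary endpoints, calculation of the Magee, Gage and Tennessee scores from patient and tumour characteristics, and adds: "These scores will also be compared with Oncotype DX ® results when performed". Section 3.8 collects "Whether ODX was ordered and if so, the ODX recurrence score", so an untested patient has no reference value. Testing is not mandated; under Section 3.3, "patients with eligible tumours will meet with their treating physician to discuss the individualised testing and treatment plan that is best for them".

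The comparison serves a declared purpose. The Summary names as unknown how the scores affect ordering, "nor how well these algorithms predict for the results of Oncotype DX ® in the real-world setting", and says the study will help to answer both. The Introduction adds: "This data will also be used to provide further validation of the algorithms in a real-world, multi-centre setting".

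Section 4.0 analyses secondary endpoints across all sites and also site by site, using chi-square or Wilcoxon tests. It does not fill in missing values unless they are obvious from other data. It names no measure of agreement or accuracy, and no weighting, tested-versus-untested comparison or sensitivity analysis for patients without an Oncotype DX result.

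**The concern.** An algorithm that predicts Oncotype DX is useful mainly for deciding who needs the test, so the population of interest is all eligible patients. The plan observes the reference result only where a physician wanted it. Physicians see the grade, size and receptor status from which the algorithms are built. If ordering depends on those features, the tested set is selected on the predictor, and sensitivity, specificity, correlation and AUC in that set need not match their values in eligible patients.

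Two features of the design make this harder to ignore. Testing rates differ sixfold between centres (15% against 90%), so the amount of selection can differ too. From month 7, physicians also receive PREDICT results, which share some inputs with the compared scores (Table 1) and are expected to change ordering. Pooling the two periods may therefore mix two selection processes.

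At stake is whether the validation result can be read as applying to eligible Ontario patients, or only to those whose physicians chose to test.

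**Working it through.** **1. The plan's own overall rate.** Inputs are the six-month volumes and baseline rates in Section 5.0. Tests = eligible × rate.

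| Centre | Eligible | Rate | Tests | Untested |
|---|---|---|---|---|
| Ottawa | 300 | 15% | 45 | 255 |
| Newmarket | 75 | 75% | 56.25 | 18.75 |
| Kingston | 75 | 65% | 48.75 | 26.25 |
| Thunder Bay | 35 | 65% | 22.75 | 12.25 |
| Windsor | 75 | 90% | 67.5 | 7.5 |
| Grand River | 75 | 90% | 67.5 | 7.5 |
| Total | 635 | | 307.75 | 327.25 |

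307.75/635 = 48.5%, which agrees with the roughly 50% assumed in Section 5.0. The annual figures in Section 4.0 (for Ottawa, "approximately 15% of approximately 600 patients treated by 8 physicians have this test performed") give 633/1300 = 48.7%.

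**2. Who makes up the tested set.**
- Ottawa: 300/635 = 47% of eligible patients, 45/307.75 = 15% of tests, 255/327.25 = 78% of the untested.
- Windsor plus Grand River: 150/635 = 24% of eligible patients, 135/307.75 = 44% of tests.

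**3. After the intervention.** Suppose the hypothesised halving of the odds applied at every site. Ottawa: odds 0.15/0.85 = 0.176 become 0.088, a rate of 8.1%. A 90% site: odds 9 become 4.5, a rate of 81.8%. Tests fall to about 245/635 = 38.6%.

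**4. Bounds without a selection model.** If a fraction t is tested and agreement among them is A, agreement in all eligible patients lies between tA and tA + (1 − t). With A = 0.80, assumed for illustration:
- pooled, t = 0.485: 39% to 90%
- a 15% site: 12% to 97%
- a 90% site: 72% to 82%

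**5. Illustration with selection models.** The documents do not say who is tested, so everything in this step is assumed: algorithm score S (standardised) and recurrence score bivariate normal, true correlation 0.70, 15% of recurrence scores high. Site intercepts are set to reproduce the Section 5.0 rates. Two shapes were tried by simulation:
- mid-range preference: logit(testing) = intercept − k(S − 0.5)², k = 0.5, 1, 2
- rising with score: logit(testing) = intercept + bS, b = 0.5, 1, 2

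| | True | Mid-range preference | Rising with score |
|---|---|---|---|
| AUC, pooled | 0.86 | 0.80-0.83 | 0.84-0.85 |
| AUC, Ottawa | 0.86 | 0.72-0.80 | 0.78-0.84 |
| AUC, 90% sites | 0.86 | 0.83-0.85 | about 0.85 |
| Correlation, pooled | 0.70 | 0.58-0.65 | 0.67-0.70 |

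If testing is unrelated to the score, there is no bias at any testing rate.

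**6. Direction.** Call the algorithm positive in its top 15%; true sensitivity is then 0.52. If the odds of testing rise 2- to 4-fold per SD of score, pooled sensitivity appears as 0.57-0.59, and as 0.67-0.76 at a 15% site. If the odds halve per SD, it appears as 0.44 and 0.33. At a 90% site it stays within about 0.01 of the truth in the rising case and reads 0.48 in the falling case. Predictive values move less: within about 0.03 pooled, and up to about 0.07 at a 15% site.

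**7. Scale against sampling error.** The Hanley-McNeil standard error of an AUC of 0.83, with 308 tests and 15% high scores, is about 0.04. The mid-range pooled loss (0.03-0.06) is of that order; the rising-case loss (0.01-0.02) is smaller.

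**The case against.** The strongest reply is that this is one sentence under secondary endpoints, absent from the objectives in Section 3.6, and that Section 4.0 already analyses secondary endpoints by site. The two 90% centres could therefore be read separately as the plan stands. That is right: the plan does not merely pool. But the by-site results are not offered as a remedy for selective testing, and nothing tells a reader that the Ottawa estimate could be the most selected.

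A reader might infer that the reported accuracy *is* distorted, or is understated. The documents do not support this. They contain no model of who is tested; bias requires ordering to depend on features tied to the score or to the result, and step 6 shows that it could run either way. Nor is the 15%-to-90% spread itself the bias. Selection within centres causes it; the spread changes its size and the mix of centres.

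A reader might also expect a misleading pre/post difference in agreement. The plan announces no such comparison, and names neither AUC nor correlation; these serve here only to show scale.

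Finally, one might want the weighted estimate to replace the pooled one. That goes too far. The average Ottawa weight is already 1/0.15 = 6.7; under the mid-range model the 99th percentile is roughly 26-42, and the pooled effective sample size is about 31% of the tests or less. Truncation brings back some bias. Section 3.8 does not link data to physicians, so physician cannot enter the weights although Section 4.0 reports marked variation between physicians. Comorbidity and patient preference are not on the collection list. Weighting recovers the true AUC almost exactly in simulation only because testing there depends solely on observed quantities.

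**Conclusion.** The point stands as a risk that the plan leaves unaddressed. About 52% of eligible patients per period (327 of 635) will have no reference result, 78% of them in one centre, while the comparison is presented as real-world validation.

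The composition figures rest only on Section 5.0. The size of any bias rests on assumptions: with correlation 0.70 and 15% high scores, the pooled AUC loss is about 0.03-0.06 under mid-range preference and about 0.01-0.02 if testing rises with score. At 90% sites the rising case leaves little bias. Sensitivity, specificity and correlation are more exposed than predictive values. The primary endpoint, the proportion of eligible patients with a test ordered, does not depend on the result and is unaffected. This should be dealt with before analysis, but it does not threaten the main question.

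**What to change.** Add to Sections 3.7 and 4.0:

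1. State that the unweighted pooled comparison describes tested patients only.
2. Present the comparison by the three testing-rate groups already defined in Section 4.0, and by period. Name Windsor/Grand River (Kitchener in Section 4.0) as the least-selected estimate: about 135 tests per period at baseline rates, 90% verified.
3. Tabulate tested against untested patients on the recorded pathology.
4. Add a sensitivity analysis weighting tested patients by the inverse of their modelled probability of testing, using centre, period, age, size, grade, receptors and, where available, Ki67, with stabilised or truncated weights and the truncation rule fixed in advance.

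The cost is analysis time only, since the pathology is collected for every eligible patient. The downsides are wider intervals, some Ottawa weights well above 7, truncation that leaves some bias, and no correction for unrecorded factors such as physician or comorbidity. The Windsor/Grand River estimate is less selected, but comes from 24% of eligible patients and need not carry over to Ottawa's case mix.
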